## 4. GENERAL METHODOLOGY

### 4.1. Analysis Sets

The analysis set will always be indicated in a subtitle in the table, listing or figure.

#### 4.1.1. All Screened Analysis Set

All subjects who signed and dated an informed consent form (ICF).

#### 4.1.2. All Randomized Analysis Set

All screened subjects who were randomized into the clinical study.

#### 4.1.3. Safety Analysis Set

All subjects who used at least 1 dose of IP.

#### **4.1.4. Full Analysis Set**

All randomized subjects who have received at least 1 dose of IP.

#### **4.1.5. Pharmacokinetic Analysis Set**

Subset of the Safety Analysis Set for which plasma concentration data are available to facilitate development of the population PK model as described in the pharmacometric analysis plan and excluding CSP deviations which have an impact on the PK analysis.

For population PK modeling, besides the plasma concentration, the corresponding PK sampling time and the time of last drug intake prior to taking the sample should be available. The results from the population PK analysis will be presented in a separate document.

[REDACTED]

[REDACTED]

[REDACTED]

[REDACTED]

[REDACTED]

#### **4.2. Randomized Versus Actual Treatment Group**

For subject information and efficacy parameters, the treatment group as assigned by the randomization will be used in the analysis (i.e. as-randomized analysis).

The actual treatment groups will be used for the analysis of safety, PK and PD parameters. The “actual” rather than “randomized” treatment will be used only in case the “wrong” drug had been taken during the entire study duration.

Differences between the randomized and actual treatment group will be listed in the disposition/randomization section of the analysis.

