7.3. Packaging, Labeling and Distribution

IP packages will be labeled with clinical study-specific details, including storage conditions.

All manufacturing, packaging, and labeling operations will be performed according to Good Manufacturing Practice for Medicinal Products and the relevant regulatory requirements.

Each medication kit will be identified with a unique kit number. Multiple kits can be provided to a subject at each visit, providing the subject with sufficient IP to cover the period until the next scheduled visit.

The distribution of IP to the site will only occur after the required local documentation is obtained, including clinical study approval by regulatory authorities and the IECs/IRBs, documentation on which the assessment of the investigator's qualifications was based (e.g. curriculum vitae), and the signed and dated study agreement and financial agreement.

To ensure study subjects maintain dosing per protocol requirements during this study special delivery services through DTP shipments of IP from the investigational site to the subject can be implemented in case of SARS-CoV-2 restrictions. DTP should only be used in case of emergency where on-site IP dispensation is not possible, and if allowed per local regulations. Local guidelines must be followed and regulatory approval or notification of authorities may be required. Agreement of the subject to receive IP at home is required prior to the shipment of IP from the investigational site to the subject's home. The DTP process used will be reviewed and approved by the sponsor, but the DTP shipments will be coordinated by the investigational site(s) in collaboration with the local CRO without the involvement of the sponsor to ensure clinical study integrity in case of SARS-CoV-2 restrictions.

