9. STATISTICAL METHODS

All statistical methods shall be detailed in a statistical analysis plan (SAP) that will be finalized prior to the database lock and unblinding. All relevant data collected in this clinical study will be documented using summary tables, figures, and subject data listings.

Any deviations from the CSP are to be justified in the SAP.

[figure not shown]

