9.3.5. Analyses of Safety Data

All safety analyses will be performed using the Safety Analysis Set (Section 9.2.4). All safety data collected on or after the first dose of IP administration up to the last contact after the last dose of IP, unless specified otherwise, will be summarized by treatment group according to the IP received. Clinical safety will be addressed by assessing AEs, laboratory assessments, physical examinations, vital signs, and 12-lead ECGs.

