### **6.1.9.2. Presentation of Results**

Summary statistics per planned treatment group and overall will be provided for each compliance and extent of exposure parameter for study drug administration. Frequency tables will be provided for the compliance parameters, using the following categories:  $<80\%$ ;  $80\% \leq x < 100\%$ ;  $100\%$ ;  $100\% < x \leq 120\%$ ;  $> 120\%$ .

All original study drug administration records will be listed per subject. The listing will include all deviations from study drug schedules such as missed or reduced doses and GLPG3970/placebo switches and will also include food intake status at the time of study drug administration.

Study drug exposure and compliance data will be listed.

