## **6.6. Changes to the Planned Analyses, Not Covered by Protocol Amendments**

- As per protocol, MMRM should have been used for primary analysis [REDACTED]. However, as the data is collected only at two time points (baseline and week 6) for the primary endpoint, the MCS, an ANCOVA with a multiple imputation method to handle missing values will be used for treatment comparison as main analysis and an analysis on observed case will be performed as sensitivity analysis. [REDACTED]

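### SAP 4.2 keeps a placebo-randomised subject with partial GLPG3970 exposure in the placebo safety column, a narrower rule than the protocol's grouping by product received

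*SAP*

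**What the plan says.** SAP 4.2 opens with a general rule: "The actual treatment groups will be used for the analysis of safety, PK and PD parameters". The next sentence restricts it. Actual treatment displaces randomised treatment only if the wrong "drug had been taken during the entire study duration". Efficacy and subject information are as randomised.

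Protocol 9.3.5 says that safety data "will be summarized by treatment group according to the IP received", and the synopsis repeats this. Neither place attaches a whole-study condition, and neither says what to do with a subject who received both products.

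The Safety Analysis Set (SAP 4.1.3) is "All subjects who used at least 1 dose of IP". This settles who is included but not the column in which they appear.

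The SAP foresees partial errors. Under SAP 6.1.9.2 the administration listing is to show "missed or reduced doses and GLPG3970/placebo switches". Those switches go to a listing and do not alter the summary tables.

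Protocol section 9 adds: "Any deviations from the CSP are to be justified in the SAP". The readable part of SAP 6.6 deals with the analysis model ("As per protocol, MMRM should have been used for primary analysis") and says nothing about treatment grouping for safety. Part of 6.6 is blacked out.

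**The concern.** The two sentences of SAP 4.2 pull against each other. The first promises actual treatment for safety. The second withdraws it for every error shorter than the whole study, so a single correctly assigned dose is enough to keep the randomised label.

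For a placebo-randomised subject, an event that began while taking GLPG3970 would then appear under placebo, which makes the drug look safer relative to placebo. Safety against placebo is a secondary objective, the placebo arm has 10 planned subjects, and protocol 5.5 describes this as the first study of GLPG3970 in UC. One subject in the wrong column is visible in a table of that size.

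**Working it through.** **Step 1. How a partial error could arise.** The protocol's Schedule of Activities shows dispensing at Visits 1, 3 and 4, and protocol 7.3 says "Multiple kits can be provided to a subject at each visit". A wrong kit at one visit would give partial exposure. SAP 4.3.2 defines one treatment period running from first dose to last contact, so nothing later in the plan splits a subject's events by product taken.

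**Step 2. The possible mix-ups under each rule.** The last column is the rule proposed under the fix.

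| Randomised | Wrong product taken | Column under SAP 4.2 | Column if any GLPG3970 dose counts |
|---|---|---|---|
| Placebo | GLPG3970 throughout | GLPG3970 | GLPG3970 |
| Placebo | GLPG3970 for part | **Placebo** | **GLPG3970** |
| GLPG3970 | Placebo throughout | Placebo | Placebo |
| GLPG3970 | Placebo for part | GLPG3970 | GLPG3970 |

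Only the second row differs, so the effect has one direction.

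**Step 3. Size.** The plan states no figure on this point, so there is none to reproduce. Inputs: 10 placebo and 20 GLPG3970 subjects planned (SAP 2.3, protocol 5.1). Suppose one placebo-randomised subject has partial GLPG3970 exposure and a TEAE only while on GLPG3970. Let a be the number with a TEAE among the other 9 placebo subjects, and b the number among the 20 GLPG3970 subjects.

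- SAP 4.2: placebo (a + 1)/10, GLPG3970 b/20.
- Any-dose rule: placebo a/9, GLPG3970 (b + 1)/21.
- Excess in the placebo rate under SAP 4.2: (a + 1)/10 − a/9 = (9 − a)/90. This is largest at a = 0, where it is 9/90 = 10 percentage points.

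The counts a and b are assumptions, since the documents give no TEAE rates:

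| a, b | SAP 4.2: placebo vs GLPG3970 | Difference | Any-dose rule: placebo vs GLPG3970 | Difference | Narrowing |
|---|---|---|---|---|---|
| 0, 4 | 1/10 = 10.0% vs 4/20 = 20.0% | 10.0 | 0/9 = 0.0% vs 5/21 = 23.8% | 23.8 | 13.8 |
| 1, 4 | 2/10 = 20.0% vs 4/20 = 20.0% | 0.0 | 1/9 = 11.1% vs 5/21 = 23.8% | 12.7 | 12.7 |
| 3, 10 | 4/10 = 40.0% vs 10/20 = 50.0% | 10.0 | 3/9 = 33.3% vs 11/21 = 52.4% | 19.0 | 9.0 |

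In these scenarios one subject narrows the GLPG3970-minus-placebo difference by 9.0 to 13.8 percentage points.

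**The case against.** The strongest reply is that the protocol does not settle the mixed case. Where a subject took one wrong product throughout, SAP and protocol agree. Where both were taken, the product received is ambiguous, and the protocol leaves statistical detail to the SAP. This stands. A reader might infer that SAP 4.2 flatly contradicts the protocol, but the documents support only that it is narrower than the protocol's plain wording.

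Second, any replacement rule also misattributes something. If a placebo-randomised subject has an event on placebo and later receives GLPG3970 in error, the any-dose rule counts that event as active. This also stands. It would be too strong to say that SAP 4.2 gives a wrong answer at every mix-up: if the event arose on placebo, or there was none, no event is misplaced.

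Third, mix-ups should be rare and would be visible. Allocation is central, kits are uniquely numbered, and SAP 4.2, 6.1.2, 6.1.3 and 6.1.9.2 list or flag discrepancies. Safety is descriptive, with no formal testing (SAP 6.3), so no test result changes. All true, but the listings leave the incidence tables as they are.

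Fourth, the safety estimand (SAP section 3) handles protocol deviations by treatment policy. That says events are counted regardless of the deviation; it does not say in which arm.

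A reader might also extend the point to PK and PD, expecting measurable drug levels in the placebo group. The documents do not support this. The PK Analysis Set excludes deviations that affect the PK analysis (SAP 4.1.5, protocol 9.2.5), and text near the analysis-set definitions, where any PD set would be described, is blacked out.

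**Conclusion.** The point holds for the adverse event, laboratory and ECG summaries. SAP 4.2 states a rule under which events arising on GLPG3970 can be reported under placebo. That rule is narrower than protocol 9.3.5 and the synopsis, and the readable text of SAP 6.6 does not declare it. Because 6.6 is partly blacked out, nothing firmer can be said about whether it was justified there.

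The size is up to 10 percentage points on the placebo TEAE rate per affected subject. That figure assumes the planned 10 placebo subjects, a placebo-to-GLPG3970 mix-up for part of the study, a TEAE while on GLPG3970, and no TEAE in that subject while on placebo. The documents report no mix-up, so this is a conditional weakness in the rule. It is not evidence that any result is wrong. The case for changing it is that the one affected configuration favours the drug and the repair is cheap.

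**What to change.** Replace the restricting sentence in SAP 4.2 with a rule for the safety summaries: a subject who received at least one dose of GLPG3970 is classified as GLPG3970, and any other treated subject as placebo. In the existing listings, flag mixed-exposure subjects and show the product being taken at AE onset, so that a reader can re-attribute events. Keep efficacy as randomised. Record the clarification in SAP 6.6, ideally before unblinding. If the sponsor prefers the whole-study condition, it should be declared and justified there as a narrowing of protocol 9.3.5.

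The cost is one sentence and a listing flag, with no new data. The downside is that a placebo-period event in a subject with brief erroneous GLPG3970 exposure is counted as active. The onset flag makes that visible, and the error is in the cautious direction for safety.

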#### **4.3. Analysis Periods and Analysis Time Points**

##### **4.3.1. Relative Day**

The timing of an assessment or an event relative to a reference date will be calculated as follows:

When the concerned date is before the reference date:

$$\text{Relative day (days)} = \text{concerned date} - \text{reference date}$$

When the concerned date is the equal to or later than the reference date:

$$\text{Relative day (days)} = \text{concerned date-reference date} + 1 \text{ day}$$

where:

- The *concerned date* could be the measurement date of the assessment, or the start or end date of the event.
- The *reference date* default is the date of the first dose of study drug administration, unless specified otherwise.
- *Date* implies a complete date having day, month and year available. Unless otherwise specified, the *relative day* will remain missing when it cannot be calculated due to absence or incompleteness of the concerned and/or reference dates.

The general terms of this formula also apply when similar relative timings are required in other time units, for example in minutes.

#### 4.3.2. Analysis Periods

For treated subjects, adverse events (AEs) and assessments will be allocated to analysis periods according to [Table 2](#).

**Table 2 Analysis Periods**

Analysis Period	Start Analysis Period	End Analysis Period
Screening	Date of signing the ICF, with 00:00 added as time part	Date (time) of first study drug administration - 1 minute
Treatment	Date (time) of first study drug administration.	Study termination date (i.e. date of last contact), with 23:59 added as time part

The last analysis period will always end on the date of last contact.

For every subject, all assessments performed and all events occurring during the study are expected to have a (start) date (/time) between the date of informed consent (IC) signature and the last contact date. Obvious exemptions are historical records like medical history or concomitant therapies having started before the study.

Assessments and events will be allocated to one of these analysis periods by incidence, meaning placing the record (start) date and time between the matching start and end dates and times of the subject's own analysis periods, assuming completeness of all dates and times, or further determined by the presence of timing indicators such as tick boxes flagging AEs starting before/after first study drug administration, or by worst-case considerations for AEs if needed. For the parameters for which the time of assessment was not planned to be collected, their assessment on the day of first IP administration will be considered as baseline and will be reported under the 'Screening' analysis period with the exception of AEs.

#### **4.3.3. Analysis Windows**

For the efficacy, PK, [REDACTED] and safety assessments, all data (including data obtained at unscheduled visits) will be placed into time windows based on the relative day (ADY) of the assessment (relative to the first dose of IP), according to the following allocation tables:

For endpoints with multiple components, analysis windows will be derived separately for each component/parameter.

**Table 3: Analysis visit window for non-PK data**

Visit date and time	Relative day (ADY)	Assessment visit (VISIT)	Time window (in ADY)*	Target day	Analysis visit (AVISIT)
On or before first study drug administration	$\leq 1$	Last assessment at any point in time before first study drug administration	$\leq 1$	1	Baseline
After first study drug administration	>1	Any scheduled (non follow-up), unscheduled, or early discontinuation visit	2 to 12	8	Week 1
			13 to 22	15	Week 2
			23 to 36	29	Week 4
			37 to 49*	43	Week 6
		Follow-up	CRF collected follow-up visit		Follow-up

\*For Week 1, Week 2, Week 3, Week 4, Week 5 and Week 6, time windows will be applied excluding assessments performed more than 2 days after the last dose of IP. Except for Endoscopy and [REDACTED] where assessments performed more than 7 days after last dose will be excluded and the Week 6 analysis window will be 37 to 52 days.

**Table 4: Analysis visit window for the daily diary data**

Visit date and time	Relative day (ADY)	Assessment visit (VISIT)	Time window (in ADY or relative to last dose of IP for the follow-up)*	Analysis visit (AVISIT)
Before first study drug administration	<1	All days before the first IP administration.	<1	Baseline
Same as or after first study drug administration	$\geq 1$	Any scheduled (non follow-up), unscheduled, or early discontinuation visit	1 to 7	Week 1
			8 to 14	Week 2
			15 to 21	Week 3
			22 to 28	Week 4
			29 to 35	Week 5
			36 to 42	Week 6
		Follow-up	1 to 7, where day 1 = first day after the last dose of IP	Week 7
			8 to 14, where day 1 = first day after the last dose of IP	Week 8

\*For Week 1, Week 2, Week 3, Week 4, Week 5 and Week 6, time windows will be applied excluding assessments performed more than 2 days after the last dose of IP.

**Table 5: Analysis Visit Window for PK data**

Visit date and time	Relative day (ADY)	Assessment visit (VISIT)	Time window (in ADY)*	Target day	Analysis visit (AVISIT)	Analysis time point (ATPT)
Before first study drug administration	<1 or pre-dose at ADY=1	Last assessment at any point in time before first study drug administration	<1 or pre-dose at ADY=1	1	Baseline	Pre-dose (within 30 minutes prior to dosing)
Same as or after first study drug administration	$\geq 1$	Any scheduled (non follow-up), unscheduled, or early discontinuation visit	1	1	Day 1	As indicated in the database: 0.5-1.5, 2-2.5, 3-4 hours post-dose
			13 to 22	15	Week 2	As indicated in the database: Pre-dose (within 30 minutes prior to dosing)
			23 to 36	29	Week 4	As indicated in the database: Pre-dose (within 30 minutes prior to dosing)
			37 to 49	43	Week 6	As indicated in the database:

Visit date and time	Relative day (ADY)	Assessment visit (VISIT)	Time window (in ADY)*	Target day	Analysis visit (AVISIT)	Analysis time point (ATPT)
						Pre-dose (within 30 minutes prior to dosing) and within [4-6 hours post dose].
		Follow-up	CRF collected follow-up visit		Follow-up	

\*For Week 1, Week 2, Week 3, Week 4, Week 5 and Week 6, time windows have to be applied excluding assessments performed more than 2 days after the last dose of IP.

**Table 6: Analysis Visit Window for urine phosphate and urine calcium**

Visit date and time	Relative day (ADY)	Assessment visit (VISIT)	Time window (in ADY)*	Target day	Analysis visit (AVISIT)	Analysis time point (ATPT)
Before first study drug administration	<1 or pre-dose at ADY=1	Last assessment at any point in time before first study drug administration	<1 or pre-dose at ADY=1	1	Baseline	Pre-dose
Same as or after first study drug administration	$\geq 1$	Any scheduled (non follow-up), unscheduled, or early discontinuation visit	1	1	Day 1	2 hours post-dose
			13 to 22	15	Week 2	
			23 to 36	29	Week 4	
			37 to 49	43	Week 6	As indicated in the database: Pre-dose and 2 hours post-dose
		Follow-up	CRF collected follow-up visit		Follow-up	

#### 4.3.4. Definition of Baseline

Baseline is defined as the last available assessment prior to the first intake of IP. For the parameters for which the time of assessment was planned to be collected, if for their assessment on the day of first intake the time is missing, their assessment at time point “PRE-DOSE” (when applicable) will be considered as baseline, otherwise, previous days last available assessment will be selected. For the parameters for which the time of assessment was not planned to be collected, their assessment on the day of first intake of IP will be considered as baseline. If multiple values qualify as last available assessment, the mean of these values will be used in the analysis.

For electrocardiogram (ECG) data assessed in triplicate, baseline is defined as the average (stored without rounding) of the combination of the most complete replicated ECG parameter before first intake of IP and at the same time the closest to it, selecting in the following order:

First consider Day 1, pre-dose:

- Select the average of the last available triplicate ECG parameter on that day;
- If there is no triplicate, select the average of the last available duplicate ECG parameter;
- In the absence of triplicates and duplicates the last available single ECG parameter will become baseline.

If baseline is not yet determined, consider the previous day and repeat the above selection (average of last triplicate, average of last duplicate, last single ECG on that day). Repeat the whole process successively for each previous day(s) as needed until baseline is determined.

For diary-based efficacy parameters, baseline is defined as the average of the values before the first IP administration. The baseline value will be derived only when there are at least 3 days with data. Otherwise, the baseline value for that parameter will be treated as missing. The definition will exclude the day prior/of/after the colonoscopy.

#### 4.3.5. Selection and Use of Analysis Visits

Before first administration of IP, only Baseline will be used for the entire statistical analysis. Pre-baseline assessments will only be listed. After first administration of IP, if multiple valid, non-missing assessments exist in an analysis window, records will be chosen based on the following rules if a single value is needed:

- The record closest to the nominal day for that visit will be selected, or
- If there are 2 records that are equidistant from the nominal day, or more than 1 record (with time known) on the selected day, the latest record will be taken
- If chronological order cannot be determined (e.g., more than 1 record on the same day with time missing), the average of the records will be computed and reported in the analysis

For the [REDACTED] endpoints including MCS, [REDACTED], the following steps will be used to derive each composite endpoint, unless otherwise specified:

- Step 1: Put [REDACTED] component value into an analysis visit window.
- Step 2: Within each visit window, select the data points for analysis.
- Step 3: Combine these selected data points within each analysis visit window across the components.

#### **4.3.6. Handling of Missing Data**

##### **4.3.6.1. Handling of Missing Date-Time Data**

No imputations will be done in case of missing date (time) fields, nor for the missing parts of partially known date (time) fields.

Assessments with missing date (time) will be omitted from the analysis.

Event-type data (e.g. AEs, concomitant medications) with missing date (time) will be allocated to analysis periods using a worst-case approach as explained in the respective sections.

